2.1.8 Biomarker endpoints

All measurements (scheduled or unscheduled) will be assigned to efficacy analysis windows defined in [Section 2.5.4](#), in order to describe all biomarkers (BM) assessments by time points even in case of premature treatment discontinuation.

Peripheral blood samples are planned to be collected for measurement of protein biomarkers at the study Visits 2 (baseline visit), Visit 6 (Week 12), Visit 7 (Week 24-EOT), Visit 8 (Week 35-EOS).

The protein biomarkers include, but are not limited to:

- Cartilage Oligomeric Matrix Protein (COMP) analyzed by Enzyme Linked Immuno Sorbent assay (ELISA) method.
- Chemokine (C-C Motif) Ligand 2 (CCL2) analyzed by ELISA method.
- Chemokine (C-C Motif) Ligand 17 - TARC analyzed by ELISA method.
- Periostin analyzed by ELISA method.
- Eotaxin-3 analyzed by Electrochemiluminescence (ECL).

2.1.9 Quality-of-life endpoints

See [Section 2.1.3.2](#).

2.1.10 Health economic endpoints

Health economic endpoints other than quality of life will be described in a separate dedicated health economics and value assessment (HEVA) statistical analysis plan.

2.2 DISPOSITION OF PATIENTS

This section describes patient disposition for both patient study status and the patient analysis populations.

Screened patients are defined as any patients who met the inclusion criteria and signed the informed consent.

Randomized patients consist of all patients with a signed informed consent form who have had a treatment kit number allocated and recorded in the IRT database, regardless of whether the treatment kit was used.

For patient study status, the total number of patients in each of the following categories will be presented in the clinical study report using a summary table:

- Screened patients.
- Screen failure patients and reasons for screen failure.
- Non-randomized but treated patients.
- Randomized patients.
- Randomized but not treated patients and reason for not being treated.
- Randomized and treated patients.
- Patients who complete and who did not complete the study treatment period as per protocol.
- Patients who discontinued study treatment sorted by main reason for permanent treatment discontinuation.
- Patients who complete and did not complete the study follow-up period as per protocol.
- Patients who discontinued study sorted by main reason for study discontinuation.
- Status at last study contact.

For all categories of patients (except for the screened and non-randomized categories) percentages will be calculated using the number of randomized patients as the denominator. Reasons for treatment and study discontinuation will be supplied in tables giving numbers and percentages by treatment group.

The cumulative incidence of premature treatment discontinuation (irrespective of the reason) and premature treatment discontinuation due to AEs will be presented graphically by treatment arm using Kaplan-Meier method. Not treated patients will be considered with event at Day 1 (day of randomization). All completers will be considered as right-censored observations. For randomized and treated patients, the time-to-event or censoring variable is defined as: last IMP administration date - randomization date + 7 days.

The cumulative incidence of premature study discontinuation will be presented graphically by treatment arm using Kaplan-Meier method. All completers will be considered as right-censored observations. The time-to-event of censoring variable is defined as:
end of study date - randomization date + 1 day, where end of study date is the date of last successful contact or visit, whichever comes last, or, for patients who died before this date, the date of death.

A patient is considered lost to follow-up at the end of the study if he/she is not assessed at the last protocol-planned visit and if the time from the last successful contact or visit, whichever comes last, to the last protocol-planned visit is greater than 2 days.

All critical or major deviations potentially impacting efficacy analyses, randomization, and drug-dispensing irregularities, and other major or critical deviations will be summarized in tables giving numbers and percentages of deviations by treatment group.

Additionally, the analysis populations for safety, efficacy, anti-SAR156597 antibody (ADA) and pharmacokinetics will be summarized in a table by number of patients on the randomized population.

- Efficacy population: intent-to-treat (ITT) population.
- Safety population.
- Anti-SAR156597 antibody population.
- Pharmacokinetics population.
- Biomarkers populations.

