1.3 DETERMINATION OF SAMPLE SIZE

The targeted treatment benefit is a difference of 4 points between treatment groups in the mean change in mRSS from baseline to Week 24.

The impact of treatment discontinuations in the context of an ITT analysis where all modified Rodnan Skin Score (mRSS) data will be included in the analysis (regardless of adherence to treatment) was evaluated. Assuming that 10% of patients will discontinue the treatment, the estimated treatment effect at 24 weeks will be decreased from 4 (targeted treatment effect if all patients adhered to treatment) to 3.6 (targeted treatment effect in all randomized patients).

Ninety four (94) patients (47 patients each in SAR156597 and placebo groups) will yield 80% power to detect a difference between SAR156597 and placebo groups of 3.6 in the mean change from baseline in mRSS at 24 weeks, assuming a Standard Deviation (SD) of 7 and using a 1 sided alpha of 5% (Type I error).

Table 1 provides power calculations depending on several assumptions for treatment effect (difference between treatment groups in the mean change in mRSS from baseline to Week 24) and SD of the response (1) (assumed to be the same in both groups (2, 3).

Table 1 - Power calculations for mRSS, depending on treatment effect and standard deviation, using a 1-sided alpha of 0.05

Treatment effect	SD	Power
$\Delta=3$	8	57%
	7	67%
	6	78%
$\Delta=3.6$	8	70%
	7	80%
	6	90%
$\Delta=4$	8	78%
	7	87%
	6	94%

Calculations were made using East 6.3 software.

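### The Day 1 event rule for never-dosed patients is not confined to the any-reason curve, so it counts them as AE-related discontinuations; the handling of non-AE stops in the AE curve is not stated

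*SAP*

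**What the plan says.** SAP 2.2 (Disposition of patients) introduces two cumulative incidence displays in a single sentence. The first is premature treatment discontinuation for any reason. The second is described as "premature treatment discontinuation due to AEs will be presented graphically by treatment arm using Kaplan-Meier method". Three rules follow, none of them tied to one curve:

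- Never-dosed patients: "Not treated patients will be considered with event at Day 1 (day of randomization".
- Censoring: "All completers will be considered as right-censored observations".
- Time variable: "For randomized and treated patients, the time-to-event or censoring variable is defined as: last IMP administration date - randomization date + 7 days".

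The same section lists a disposition row for "Randomized but not treated patients and reason for not being treated" and a breakdown of discontinuations by main reason, with numbers and percentages by arm. The information needed to classify a never-dosed patient is therefore collected, but it does not enter the definition of the AE event. No competing-risk estimator is named.

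**The concern.** For the any-reason curve, counting a never-dosed patient as discontinued on Day 1 is defensible. For the AE curve the same rule gives a wrong classification: a patient who never received study drug appears as a stop caused by an AE.

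That conflicts with the rest of the SAP. The treatment-emergent period in SAP 2.1.5 starts at first administration. The safety population in SAP 2.3.2 requires at least part of one dose, apart from patients whose intake is unclear. The tables of treatment-emergent AEs leading to discontinuation in SAP 2.4.5.1 rest on that population. If an arm has a never-dosed patient, the curve and these tables will disagree.

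Such patients are possible. SAP 2.2 defines randomisation by kit allocation, whether or not the kit is used. In the order recommended in Protocol 10.1.2, the randomisation call precedes the laboratory tests, ECG, lung function tests and first dose.

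There is also a gap. The SAP names only completers as censored. A patient who stops for a non-AE reason has no AE event, and the time variable ends at last dose plus 7 days, so the natural implementation censors that patient there. The resulting curve would not strictly be the cumulative incidence it is labelled as. What is at stake is the presentation of tolerability by arm. Safety is a secondary objective (SAP 1.2.2), and this is the only time-to-event display of AE-related stopping in the plan.

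**Working it through.** **Inputs from the documents.** SAP 1.3 gives "47 patients each in SAR156597 and placebo groups" and the assumption "Assuming that 10% of patients will discontinue the treatment". For one arm, 0.10 × 47 = 4.7, so about 5 patients. The SAP gives no split into AE and other reasons and no expected number of never-dosed patients.

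**The plan's own figure.** None is given for these curves. The design figure in SAP 1.3 ("will yield 80% power to detect a difference between SAR156597 and placebo groups of 3.6") reproduces: 3.6 / (7 × √(2/47)) = 2.493; 2.493 − 1.645 = 0.848; Φ(0.848) = 80.2%. The present point does not depend on it.

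**Assumptions.** The counts of AE stops, other stops and never-dosed patients are mine. Stops are interleaved over the treatment period, and everyone else completes. Two scenarios are used: 2 AE and 3 other stops (close to the planned 10%), and 5 AE and 10 other stops (15/47 = 32%, well above plan).

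**Formulas.** One minus Kaplan-Meier is 1 − ∏(1 − d/r), with d the AE events and r the number at risk at each event time. With non-AE stops and never-dosed patients as competing events and no censoring before the last stop, the Aalen-Johansen estimate ends at AE stops / 47.

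**Step 1: effect of the Day 1 rule.** One never-dosed patient produces a step of 1/47 = 2.13 points on Day 1.

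**Step 2: 2 AE and 3 other stops, in the order other, other, AE, other, AE.**

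- Competing-risk value: 2/47 = 4.26%.
- No never-dosed patient: 1 − (44/45)(42/43) = 4.50%. The gap of 0.24 points comes from censoring alone.
- One never-dosed patient: 1 − (46/47)(43/44)(41/42) = 6.63%.

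**Step 3: 5 AE and 10 other stops, as other, other, AE repeated five times.**

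- Competing-risk value: 5/47 = 10.64%.
- No never-dosed patient: 1 − (44/45)(41/42)(38/39)(35/36)(32/33) = 12.32%. The gap from censoring is 1.7 points.
- If all 10 other stops came first: 1 − 32/37 = 13.51%, a gap of 2.9 points.

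**End of the AE curve in one arm under the rules as written, with non-AE stops censored:**

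| Never-dosed patients in the arm | 2 AE, 3 other | 5 AE, 10 other |
|---|---|---|
| 0 | 4.50% | 12.32% |
| 1 | 6.63% | 14.49% |
| 2 | 8.76% | 16.67% |
| 3 | 10.90% | 18.85% |
| Competing-risk value | 4.26% | 10.64% |

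Both effects are upward. Near the planned discontinuation rate, the Day 1 rule is much the larger once any patient is undosed.

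**The case against.** Randomisation and first dose fall at the same visit, after eligibility is confirmed, so never-dosed patients should be few and may be none. With none, the main effect vanishes. The curves carry no test, and SAP 2.4.5 describes the safety analysis as essentially descriptive. Correct counts are planned in the disposition tables of SAP 2.2 and the discontinuation tables and listing of SAP 2.4.5.1. A reader who saw a step at Day 1 could trace it to the not-treated row. All of this stands. It limits the importance of the point, but it does not make the rule right for the AE curve.

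A patient left undosed because of a pre-treatment AE might reasonably be counted. The rule does not make that distinction, and SAP 2.4.5.1 already provides a listing for pre-treatment AEs leading to discontinuation.

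A reader might infer that the SAP has a written rule censoring non-AE stops. It does not. Censoring is stated for completers only, and the rest is inferred from the Kaplan-Meier method and the time variable. The accurate criticism is that the handling is unstated.

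**Conclusion.** The Day 1 rule is wrong for the AE curve as written. It adds about 2.1 points per never-dosed patient to that arm's curve, and nothing if every randomised patient is dosed. The unstated handling of non-AE stops is a smaller matter: if they are censored, the overstatement is about 0.2 points with an assumed 2 AE and 3 other stops, and about 1.7 points with an assumed 5 and 10.

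A reader might go further and infer that the plan inflates AE-related stopping by a large proportion, or that it could create or hide a tolerability difference. The documents do not support that. With 3 AE stops, 4 other stops and 1 never-dosed patient, the curve ends at 1 − (46/47)(43/44)(41/42)(40/41) = 8.9% against 3/47 = 6.4%, about 40% higher in relative terms. That ratio comes mostly from one assumed undosed patient over a base of three events; censoring alone gives 1 − (44/45)(42/43)(41/42) = 6.8%. The example also has 8 of 47 patients (17%) off treatment, above the planned 10%. The comparison between arms shifts only if the number of undosed patients differs between them. The curve feeds no test, and the primary analysis is untouched. This is a minor correction worth making.

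**What to change.** In SAP 2.2:

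1. Confine the Day 1 event rule to the any-reason curve. This removes the larger error and needs one sentence and no new method.
2. For the AE curve, do not count never-dosed patients as AE events. Either treat them as a competing event, which keeps 47 as the denominator, or restrict the curve to treated patients. In the first scenario with one undosed patient these give 2/47 = 4.26% and 2/46 = 4.35%.
3. State how non-AE discontinuers enter the AE curve, and estimate it by the Aalen-Johansen cumulative incidence with non-AE discontinuation as the competing event, so that the display matches its label.

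The cost is two or three sentences and the programming of one figure. No extra data are needed, because SAP 2.2 already tabulates the reasons for non-treatment and for discontinuation. The SAP names no procedure for these curves and specifies only SAS 9.0 or higher, so the programming effort for item 3 should be confirmed.

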2.2.1 Randomization and drug dispensing irregularities

Randomization and drug-dispensing irregularities occur whenever:

1. A randomization is not in accordance with the protocol-defined randomization method, such as
 - a) An ineligible patient is randomized,
 - b) A patient is randomized based on an incorrect stratum, or
 - c) A patient is randomized twice.

OR
2. A patient is dispensed an IMP kit not allocated by the protocol-defined randomization, such as
 - a) A patient at any time in the study is dispensed a different treatment kit than as randomized (which may or may not contain the correct-as-randomized IMP), or
 - b) A non-randomized patient is treated with IMP reserved for randomized patients.

Randomization and drug-dispensing irregularities will be monitored throughout the study and reviewed on an ongoing basis.

All randomization and drug-dispensing irregularities will be documented in the clinical study report. If the number of irregularities is large enough to make a tabular summary useful, the irregularities will be categorized and summarized among randomized patients (number and percentages). Non-randomized, treated patients will be described separately.

Randomization and drug-dispensing irregularities to be prospectively identified include but are not limited to:

Randomization and drug allocation irregularities

Kit dispensation without IRT transaction

Erroneous kit dispensation (IMP number actually administered to the subject is different from the IMP number allocated by IRT)

Kit not available

Stratification error (Wrong stratum of randomization)

Patient switched to another site

Randomization of a non-existent subject

2.3 ANALYSIS POPULATIONS

Patients treated without being randomized will not be considered randomized and will not be included in any efficacy population. The safety experience of these patients will be reported separately, and these patients will not be in the safety population.

The randomized population includes any patient who has been allocated to a randomized treatment regardless of whether the treatment kit was used.

For any patient randomized more than once, only the data associated with the first randomization will be used in any analysis population. The safety experience associated with any later randomization will be assessed separately.

The safety experience of patients treated and not randomized will be reported separately, and these patients will not be in the safety population.

2.3.1 Efficacy populations

2.3.1.1 Intent-to-treat population

The intent-to-treat population is defined as all randomized patients. Patients in the ITT population will be analyzed according to the treatment group allocated by randomization.

2.3.2 Safety population

The safety population is defined as randomized patients who actually received at least 1 dose or part of a dose of the IMP, analyzed according to the treatment actually received.

In addition:

- Randomized patients for whom it is unclear whether they took the IMP will be included in the safety population as randomized.
- For patients receiving more than 1 IMP during the trial, the treatment group allocation for as-treated analysis will be the one received in the majority of injections.

2.3.3 Anti-SAR156597 antibody (ADA) population

The anti-SAR156597 antibody analysis will be performed on all randomized and treated patients (safety population) with at least one baseline and post dose ADA sample with a reportable result. Patients will be analyzed according to the treatment actually received.

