9.3.1.3.2 Anti-drug antibodies

All ADA samples will be analyzed by the Bioanalysis and Biomarkers domain in DSAR OC Montpellier (France).

For the analysis of potential ADAs in human plasma, a validated bridging qualitative ELISA using electrochemiluminescence detection will be used.

Positive samples in screening assay will then be tested in a confirmatory assay (competition with SAR156597) in order to demonstrate the presence of antibodies and eliminate false positive results generated from the initial screening assay.

Interference of SAR156597 in the ADA assay will be documented so that the highest drug concentration that does not affect the limit of ADA detection is known, and the interpretation of immunogenicity takes into account this parameter.

Additional information on the bioanalytical method for ADAs will be provided in the Laboratory Manual.

Samples that are ADA positive will be further evaluated for their potential neutralizing activity with an assay currently in development.

Placebo samples will only be analyzed at baseline, and will continue to be followed if the baseline time point results positive for ADA.

In the interim, the Sponsor will store frozen specific aliquots for neutralizing activity testing if necessary.

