11.3.3 Anti-SAR156597 antibody (ADA) population

The anti-SAR156597 antibody analysis will be performed on all randomized and treated patients (safety population) with at least 1 post dose ADA sample with a reportable result. Patients will be analyzed according to the treatment actually received.

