11.4.4 Analysis of immunogenicity

The analysis of immunogenicity will be performed on the ADA population. It will include summaries for ADA prevalence, treatment-boosted ADA incidence, treatment-induced ADA incidence and kinetics of the immune response in patients with treatment-induced ADAs. Impact on PK, efficacy and safety will be assessed. Further details will be provided in the SAP.

Please refer to [Section 9.3](#) for the detection of ADA.

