2.1.7 Immunogenicity variables

All measurements (scheduled or unscheduled) will be assigned to analysis windows defined in [Section 2.5.4](#), in order to provide an assessment of the Anti-SAR156597 antibodies (ADA) parameter at each time point planned to be collected as per protocol.

ADA positive patients are patients with at least 1 treatment-induced or treatment-boosted ADA positive sample during the TEAE period, where:

- Treatment induced ADAs: ADAs developed de novo (seroconversion) following administration of the biotherapeutic (ie, formation of ADAs any time after the initial drug administration in a subject without pre-existing ADAs). If the baseline ADA sample is missing or non-reportable and at least one reportable ADA sample is available during the treatment (including follow-up period) the baseline sample will be considered as “negative” for data analysis. This is considered being a conservative approach for ADA assessment.

- Treatment boosted ADA: Pre-existing ADAs that were boosted to a higher level following administration of biotherapeutic (ie, any time after the initial drug administration) the ADA titer is significantly higher than the baseline titer. A low serial dilution schema (2-fold or 3 fold) should be applied during titration. A difference in titer values of two titer steps between an on treatment or follow-up sample and its baseline sample is considered significant. For examples, at least a 4-fold increase in titers for 2-fold serial dilution schema (or 9-fold increase in titers for 3-fold serial dilution schema). If no titer could be determined for a positive sample, the titer will be reported as the MRD of the assay.

The rest will be classified as ADA negative or inconclusive patients.

The following variables will be described:

- ADA response (Positive, Negative or inconclusive). For ADA positive:
 - Titer levels,
 - Neutralizing status (Positive or inconclusive).
- Pre-existing positive ADA defined as patients with positive ADA response at baseline with less than a specific increase (depending on titer calculation, eg, 4-fold increase in titer for 2-fold serial dilution schema, 9-fold increase in titer for 3-fold serial dilution schema) in the post-baseline period.

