- Treatment-emergent positive ADA response defined as 1) Patients with no ADA positive response at baseline but with any positive response in the post-baseline period (up to follow-up visit) or 2) Patients with a positive ADA response at baseline and at least a specific increase (depending on titer calculation, eg, 4-fold increase in titer for 2-fold serial dilution schema, 9-fold increase in titer for 3-fold serial dilution schema) in titer in the post-baseline period (up to follow-up visit). For treatment-emergent positive ADA, the following categories for ADA duration will be applied:
 - A persistent positive response is a treatment-emergent ADA positive response detected in at least 2 or more post-baseline samples separated by at least a 16-week period (irrespective of any negative sample in between),
 - An indeterminate duration positive response is defined as ADA present only at the last sampling time point (and all previous samples negative) or with two last samples are positives but separated by a period less than 16 weeks.
- A transient positive response is defined as
 - Treatment induced ADA detected only at one sampling time during treatment or follow-up observation period (excluding last sampling time),
 - Treatment induced ADA detected at two or more sampling time during treatment where the first and last ADA positive sample are separated by a period less than 16 weeks and last sampling time is negative.
- Duration of ADA defined as longevity of treatment induced ADA (in days): date of last treatment induced ADA sample minus date of first treatment induced or treatment boosted ADA sample + 1. This will be calculated only for subjects with at least 2 positive ADA samples.
- Time to onset of treatment-emergent ADA positive response (in days): date of first ADA positive - date of first IMP administration.

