2.4.7 Analyses of immunogenicity data

The following summaries will be performed on the ADA population, taking into account all samples regardless of timing in relation to injections:

- ADA results (negative, positive or inconclusive) by time point and by treatment arm.
- Neutralizing status (inconclusive or positive) for positive ADA by time point and by treatment arm.

- ADA titers using descriptive statistics (median, Q1, Q3, minimum and maximum) for positive ADA by time point and by treatment arm.
- Number (%) of patients with pre-existing ADA and number (%) of patients with treatment-emergent ADA positive response by treatment arm.
- Number (%) of patients with persistent/transient/indeterminate treatment-emergent ADA positive response by treatment arm.
- Time to onset of treatment-emergent ADA positive response (in days) using descriptive statistics by treatment arm and also according to peak titer.
- Duration of ADA (in days, only for subjects with at least 2 positive ADA samples) using descriptive statistics by treatment arm.

Correlations between ADA parameters (eg, titers, treatment-emergent ADA positive status, neutralizing status) and PK, safety and/or main efficacy endpoint(s) will be explored (eg, scatter plot) according to the study results.

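### The placebo ADA population is in effect selected on a positive baseline result, so placebo baseline ADA prevalence reads about 100% by construction and placebo treatment-emergent ADA cannot be interpreted

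*SAP*

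**What the plan says.** **Assay rule.** Protocol 9.3.1.3.2: "Placebo samples will only be analyzed at baseline, and will continue to be followed if the baseline time point results positive for ADA".

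**Analysis population.** Protocol 11.3.3 takes the safety population "with at least 1 post dose ADA sample with a reportable result". SAP 2.3.3 adds a baseline requirement: "with at least one baseline and post dose ADA sample with a reportable result". Both need a post-dose result, and neither treats placebo differently.

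**Outputs.** Protocol 11.4.4 runs the immunogenicity analysis on this population: "It will include summaries for ADA prevalence, treatment-boosted ADA incidence, treatment-induced ADA incidence and kinetics of the immune response". SAP 2.4.7 does the same and splits by arm. Its rows include "ADA results (negative, positive or inconclusive) by time point and by treatment arm" and "Number (%) of patients with pre-existing ADA and number (%) of patients with treatment-emergent ADA positive response by treatment arm", then a row dividing treatment-emergent responses into persistent, transient and indeterminate.

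**Definitions (SAP 2.1.7).** Pre-existing: "Pre-existing positive ADA defined as patients with positive ADA response at baseline with less than a specific increase". Treatment-emergent, first route: "Patients with no ADA positive response at baseline but with any positive response in the post-baseline period". The second route is a positive baseline followed by a sufficient rise in titer.

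The placebo assay rule does not appear in SAP 2.1.7, 2.3.3 or 2.4.7, and the changes recorded in SAP 1.5 and 1.6 do not touch it.

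**The concern.** The assay rule and the population rule do not fit together. A placebo patient who is negative at baseline has no scheduled post-dose result, so either population definition removes that patient. The placebo column is then selected on the very variable it reports.

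Baseline prevalence in the placebo arm can be known correctly, because every placebo baseline sample is to be assayed. The stated rules set most of those results aside and tabulate a figure near 100%.

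The treatment-emergent rows have a different problem. Conversion from negative to positive is not looked for in placebo patients who start negative, so a placebo percentage there describes only the few who started positive. A reader who wants background reactivity in untreated patients, to put the SAR156597 rates in context, would be misled by the first figure and could not use the second. SAP 2.2 will also print the size of the ADA population, so a very small placebo count would appear with no explanation in the SAP.

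**Working it through.** **Inputs**

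- Planned placebo patients: 47 (Protocol 6.1 and 11.1).
- Assay and population rules: as set out above.
- Baseline ADA prevalence *p*: not given. The 4 of 36 in the Protocol introduction is a post-dose count in healthy subjects who received SAR156597, so it cannot serve. I assume 2%, 5%, 10% and 15%.
- Simplifications: all 47 are treated and have a reportable baseline, each baseline-positive patient has a reportable post-dose result, and no unscheduled sample brings in a baseline-negative patient.

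**The plan's own figure.** With a difference of 3.6, SD 7, one-sided alpha 5% and 80% power, the normal-approximation formula gives 47 per group. Power at 47 per group is 0.802 (0.797 with the noncentral t). The 47 is reproduced. The plan states no ADA figure to reproduce.

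**Step 1: who is in the placebo column.** If *k* of 47 placebo patients are positive at baseline, only those *k* have a post-dose result. The placebo ADA population is *k*, not 47.

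**Step 2: its expected size.** Expected size = 47*p*. Expected number excluded = 47(1 − *p*). Chance of an empty column = (1 − *p*)^47.

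| Assumed *p* | Expected in column | Expected excluded | Chance column is empty |
|---|---|---|---|
| 2% | 0.94 | 46.06 (98%) | 0.98^47 = 38.7% |
| 5% | 2.35 | 44.65 (95%) | 0.95^47 = 9.0% |
| 10% | 4.70 | 42.30 (90%) | 0.90^47 = 0.7% |
| 15% | 7.05 | 39.95 (85%) | 0.85^47 = 0.05% |

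**Step 3: what the baseline row shows.** As planned it is *k*/*k* = 100% for any *k* of 1 or more, and 0/0 if *k* = 0. Over all patients with a baseline result it is *k*/47:

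| *k* | As planned | Over 47 |
|---|---|---|
| 1 | 100% | 2.1% |
| 2 | 100% | 4.3% |
| 3 | 100% | 6.4% |
| 5 | 100% | 10.6% |
| 7 | 100% | 14.9% |

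**Step 4: what the pre-existing and treatment-emergent rows show.** Every patient in the column was positive at baseline. Each is therefore either pre-existing (no sufficient titer rise) or treatment-emergent by the second route (sufficient rise), and the two add to 100%. The first route needs a negative baseline, and the column has no such patient. A single boosted placebo patient would print as 100%, 50%, 33.3%, 20% or 14.3% for *k* = 1, 2, 3, 5 or 7. Dividing by 47 instead (2.1%) would not be an estimate either, because conversion among the other 47 − *k* patients was never assayed. The persistent/transient/indeterminate row inherits the same limit.

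**The case against.** **The placebo restriction is deliberate and stated.** True, and it is not in dispute. The difficulty is a population rule and by-arm tables that take no account of it.

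**Baseline-negative placebo patients can still enter.** Protocol 10.6.3.2 asks for an unscheduled ADA sample after allergic events with skin involvement or progressing injection site reactions, in either arm, and SAP 2.4.7 uses samples whatever their timing. The documents do not settle whether such placebo samples would be assayed, and the Laboratory Manual is not available here. This stands: it would be too strong to say that only baseline-positive placebo patients can ever appear. But those admitted this way would be selected on an adverse event, so the column would still not represent the arm.

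**A post-dose result is a sensible requirement for an incidence.** Also right. A reader might infer that the treatment-emergent percentages simply have the wrong denominator. They do not; placebo incidence is not assessed. Only the baseline prevalence has a denominator that can be corrected.

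**No zero for treatment-induced ADA is listed.** A reader might expect the SAP to print a placebo zero for induced ADA. SAP 2.4.7 has no such row. Protocol 11.4.4 promises induced incidence but does not say by arm, and one definition in SAP 2.1.7 ties induced ADA to receiving the biotherapeutic. That reading is not supported.

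**Nothing depends on the placebo column.** Correct. The immunogenicity objective concerns SAR156597, and a handful of placebo patients beside a nearly full active arm would be conspicuous. This limits the severity but does not make the figure right.

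**Conclusion.** The point holds and is minor. Following the rules as written, placebo baseline ADA positivity is reported as about 100%, or the column is empty, although the correct proportion can be computed from results already due to be assayed. The direction does not depend on the assumed prevalence; the size does. At 2% to 15%, the expected placebo denominator is 0.9 to 7.1 of 47, under the simplifications listed in the working. Placebo treatment-emergent percentages, including the persistent/transient/indeterminate split, are not interpretable, and no choice of denominator changes that. SAR156597 rates, efficacy analyses and all tests are untouched.

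A related inconsistency concerns the baseline requirement. SAP 2.1.7 counts a missing or non-reportable baseline as negative, SAP 2.3.3 requires a reportable baseline, and Protocol 11.3.3 does not. A reader might infer that the missing-baseline rule has no patient to apply to. That goes too far: Protocol 9.3.1.1 schedules pre-dose ADA samples at both Visit 1 and Visit 2, so the answer depends on which sample counts as baseline, and the rule does have patients under Protocol 11.3.3.

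**What to change.** In SAP 2.3.3 and 2.4.7:

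1. Report baseline ADA prevalence in both arms over all treated patients with a reportable baseline result. SAP 2.3.5 already defines a baseline population of this kind for biomarkers.
2. Report treatment-emergent percentages, including persistent/transient/indeterminate, for SAR156597 only. Mark the placebo entries as not assessed, and list individually the placebo patients who have post-dose results.
3. Footnote these tables with the placebo assay rule and its source, Protocol 9.3.1.3.2.

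Separately, state which pre-dose sample is the ADA baseline, and reconcile SAP 2.3.3 with the missing-baseline rule in SAP 2.1.7 and with Protocol 11.3.3.

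The cost is SAP wording, one extra denominator, a short listing and a footnote, with no new samples or assays. The price is that no placebo treatment-emergent percentage appears, but the design does not measure one.
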